11.1.2. Clinical Laboratory Data Analyses

For hematology and serum chemistry tests, the mean, mean change, median, median change, and range of all values for each test for each treatment group at baseline and for the final 'on therapy' values will be printed in a summary table. A second table (a 'shift table') will be made, showing for each laboratory variable the percentage of subjects in each treatment group whose values decreased, stayed the same, or increased between the baseline or pre-treatment period and the end of the study. A third table will be prepared displaying the numbers of subjects in each treatment group who had values below, within, and above the normal range at baseline and at the final visit.

These tables will be reviewed by the PI or RM/ISM to evaluate whether any significant trends in laboratory values occurred. The PI or RM/ISM will also review the urinalysis data by inspecting the laboratory data tabulations, but no summary tables of these will be prepared.

11.2. Planned Enrollment and Reason for Sample Size

The study will enroll 6 randomized groups of 12 subjects each, for a total of 72 subjects. Due to COVID restrictions, 10 subjects from Group 6 may be replaced to ensure completion of the 3 series dose of vaccine. This will account for a total of 82 subjects. This approach will ensure at least 60 subjects complete all vaccinations at around 10 subjects per group, taking possible attrition into account. Subjects will receive one dose of vaccine on Days 0, 28, and 56 and will be followed until Day 220.

The proposed study size is appropriate for a Phase 1 study. A Phase 1 study is designed to evaluate preliminary human safety data but not designed to show statistically significant differences between the groups.

Thus at least 7/10 or 8.4/12 subjects must seroconvert to establish a true seroconversion rate of no less than 30% with 95% confidence.

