4.4.2. Clinical Studies

4.4.2.1. Phase 1 Study to Evaluate the Safety, Tolerability, and Immunogenicity of Hantaan and Puumala Virus DNA Vaccines, pWRG/HTN-M(x) and pWRG/PUU-M(s2), for Prevention of Hemorrhagic Fever with Renal Syndrome Administered to Healthy Adult Volunteers Using the TDS-IM Electroporation Delivery Device (S-11-12, WRAIR 1854)

The HTNV DNA and PUUV DNA vaccine products were previously administered to 31 healthy human subjects via the Ichor EP device in a Phase 1 study conducted at the Walter Reed Army Institute of Research, Silver Spring, Maryland, from January 2012 to January 2013 ([Hooper, et al, 2014](#)). In this study, 27 subjects received 3 doses at 2 mg/mL per dose of HTNV DNA vaccine, PUUV DNA vaccine, or a combination of HTNV DNA and PUUV DNA vaccines over a 2-month period by IM injection. Two other subjects received 2 doses of the HTNV DNA vaccines and 2 subjects received 1 dose of the HTNV/PUUV DNA vaccine.

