The study may enroll 6 randomized groups of 12 subjects each for a total of 82 subjects (This accounts for 10 replacement subjects for Group 6, impacted by COVID). The study had initially planned to enroll 6 randomized groups of 12 subjects each, for a total of 72 subjects. Ten subjects in Cohort 6 may be replaced because vaccination and data collection were negatively impacted in this group by COVID-19 pandemic quarantine restrictions. This approach will ensure at least 60 subjects complete all vaccinations at around 10 subjects per group, taking possible attrition into account. Subjects will receive one dose of vaccine on each of Days 0, 28, and 56 and will be followed until Day 220.

The HTNV and PUUV DNA vaccines will be administered to subjects as follows:

Group 1⁴: 0.6 mg HTNV by ID EP

⁴ Sentinel subjects will not be included for Groups 1 and 3 because the dose is lower than the 2.0 mg/mL dose that was previously evaluated for these products.

Group 2: 3.0 mg HTNV by IM EP

Group 3: 0.6 mg PUUV by ID EP

Group 4: 3.0 mg PUUV by IM EP

Group 5: 1.2 mg HTNV/PUUV by ID EP

Group 6: 6.0 mg HTNV/PUUV by IM EP

Every subject will receive 1 injection on Days 0, 28, and 56 for a total of 3 injections.

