The first study enrollment activities will involve selection and randomization of volunteers as sentinels for Groups 2 and 4, and then subjects for the remainder of the Group 2 and 4 cohort. The sentinel subjects for Groups 2 and 4 (n = 2 per group, or 4 total) will be vaccinated and evaluated for 48 hours prior to dosing the remainder of Group 2 and 4 (n = 10 per group, or 20 total). After the first dose for all subjects in Groups 2 and 4 has been successfully completed and none of the halting criteria are met, then the first dose will be given to 2 sentinel subjects in Group 6 (n=2 , total of 2 subjects) on the same day, and those 2 subjects will be followed for 48 hours as per the Sentinel Group Halting Rules. The SRC will meet and evaluate the safety data collected in the 48-hour period post-vaccination for sentinels in Group 6. If the SRC finds that the halting rules have been met (Section 6.6.1.1), the PI will notify ORA PSSO within 24 hours. An SMC meeting will be held to conduct a review of clinical and laboratory safety and reactogenicity data. After the meeting, the SMC will make its recommendations in writing regarding continuation, modification, or termination of the clinical trial. If the recommendation is to proceed, enrollment, randomization, and vaccination (Day 0) of the remaining volunteers in Group 6 (n=10 per group). The first dose will be given to 2 sentinel subjects in Group 5 (n=2, total of 2 subjects) on the same day and those 2 subjects will be followed for 48 hours as per the Sentinel Group Halting Rules. The SRC will meet and evaluate the safety data collected in the 48-hour period post vaccination for sentinels in Group 5. If the SRC finds that the halting rules have been met (Section 6.6.1.1) the PI will notify ORA PSSO within 24 hours. A SMC meeting will be held to conduct a review of clinical and laboratory safety and reactogenicity data. After the meeting, the SMC will make its recommendations in writing regarding continuation, modification, or termination of the clinical trial. If the recommendation is to proceed, enrollment, randomization, and vaccination (Day 0) of the subjects in Groups 1 and 3 (n=12 per group, total of 24 subjects) will commence. Subjects in Groups 1 and 3 will be evaluated for the 48-hours post-vaccination for any halting criteria on the Day 2 clinic visit (Table 4). After completion of enrollment and first vaccination for Groups 1 and 3, the remaining subjects for Group 5 and ten Group 6 replacements (total of 20 subjects) may be enrolled, randomized and vaccinated (Day 0), provided that the enrollment of these 20 subjects can be completed within 4 months (see randomization schedule in Appendix B). Subjects are expected to complete a total of 11 visits (not including screening). There will be a 6 month follow-up after the final injection (Day 220). Overall study duration is expected to be approximately 8 months.

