7.5.4. Replacement of Subjects

To ensure that a required minimum number of subjects (60) complete key study events for purposes of statistical analysis, 6 randomized groups of 12 subjects each will be enrolled, for a total of 82 subjects. If a subject is deemed ineligible or withdraws prior to enrollment/first dose (study Day 1) they will be replaced to ensure 82 subjects are enrolled. This approach will ensure at least 60 subjects complete all vaccinations at around 10 subjects per group, taking possible attrition into account from the start of the study.

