APPENDIX B. SENTINEL SUBJECT ENROLLMENT PROCESS

Randomization Figure pertaining to Amendments 1.0-4.0 (maintained in this document for reference).

Randomization Figure pertaining to Protocol Version 6.0 and future versions. These activities will proceed since completion of enrollment and vaccinations for Groups 2 and 4 and sentinels for Group 6 (n=36 already enrolled by March of 2020). The Randomization Scheme describes plan for enrollment in Nov 2021 of sentinel participants in Group 5 (n=2), then enrollment of Groups 1 and 3 (n=24) and Groups 5 and 6 (n=20).

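### Protocol 11.2 says the design will ensure at least 60 completers at about 10 per group, but the last 20 subjects are conditional; without them Group 5 has 2 subjects and at most 52 to 62 can complete

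*Protocol*

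**What the plan says.** - **The guarantee.** Protocol 11.2 states: "This approach will ensure at least 60 subjects complete all vaccinations at around 10 subjects per group". The Synopsis (Methodology), 6.2 and 7.5.4 carry the same sentence. Section 7.5.4 describes 60 as the required minimum for statistical analysis.
- **The base.** Section 11.2: "The study will enroll 6 randomized groups of 12 subjects each, for a total of 72 subjects". It adds that "10 subjects from Group 6 may be replaced to ensure completion of the 3 series dose of vaccine", which brings the total to 82. Section 6.2 gives the reason: "vaccination and data collection were negatively impacted in this group by COVID-19 pandemic quarantine restrictions".
- **The condition.** Section 6.2 and the Synopsis say the remaining Group 5 subjects and the ten Group 6 replacements may be enrolled after Groups 1 and 3, "provided that the enrollment of these 20 subjects can be completed within 4 months".
- **Progress.** Appendix B gives "n=36 already enrolled by March of 2020", then plans 2 Group 5 sentinels, 24 subjects in Groups 1 and 3, and 20 in Groups 5 and 6.
- **Replacement.** Section 7.5.4 replaces subjects found ineligible or lost before the first dose. Apart from the ten Group 6 replacements, no rule covers later loss. The same section states "6 randomized groups of 12 subjects each will be enrolled, for a total of 82 subjects".

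**The concern.** A result that depends on an uncertain enrolment window is not ensured, and no section gives the number of completers if the window is missed. The shortfall would not be spread evenly: ten of the 20 conditional subjects are ten of Group 5's twelve, and the other ten are all of the Group 6 replacements. These are the two combination groups, on which the first secondary objective (combination relative to monovalent vaccine) depends. Completion also matters for analysis, because SAP 6.4 leaves subjects who withdrew out of the final overall seroconversion rate. Separately, the head count quoted from 7.5.4, and its counterpart in 6.2, does not add up.

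**Working it through.** **1. Reproduce the plan's figures.**
- Enrolment: 72 + 10 = 82. By group, 5 × 12 + 22 = 82. By Appendix B, 36 + 2 + 24 + 20 = 82, where 36 = 12 + 12 + 12 for Groups 2, 4 and 6.
- Completers: SAP 4.1 enrols 12 per group with the aim that 10 complete, so 6 × 12 × 10/12 = 60. The stated 60 is reproduced, but only with the conditional 20 included.
- The count in 6.2 and 7.5.4: 6 × 12 = 72, not 82.

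**2. Conditional 20 not enrolled.**
- Enrolled: 82 − 20 = 62.
- Let k be the number of the ten affected Group 6 subjects who received all three doses.
- Maximum completers with no other loss, Groups 1 to 6 in order: 12 + 12 + 12 + 12 + 2 + (2 + k) = 52 + k. With k from 0 to 10 this is 52 to 62.
- Reaching 60 needs k ≥ 8. At k = 8 nobody else may be lost; at k = 10 at most 2 of the other 52 may be lost.
- With the plan's own 10/12 retention in Groups 1 to 4 and no loss among the sentinels: 40 + 2 + 2 + k = 44 + k, so 44 to 54. This is below 60 for every k.
- Group 5 has 2 subjects whatever k is.

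**3. Conditional 20 enrolled.** With k = 0, 82 − 10 = 72 subjects can complete. The plan states no dropout rate, so a range is assumed. X is binomial (72, 1 − dropout):

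| Assumed dropout | P(X ≥ 60) |
|---|---|
| 5% | 1.00 |
| 10% | 0.975 |
| 15% | 0.72 |
| 16.7% (the plan's implied 2 of 12) | 0.58 |
| 20% | 0.30 |
| 25% | 0.06 |

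For reference, Protocol 4.4.2.1 reports that "27 subjects received 3 doses at 2 mg/mL per dose of HTNV DNA vaccine", PUUV or the combination, out of 31 dosed. At 27/31 = 87%, the expected number is 72 × 27/31 = 62.7 and P(X ≥ 60) = 0.87. That trial used the IM route only, so it is a guide and not a rate for this study.

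**4. What a Group 5 of 2 can show.**
- Exact (Clopper-Pearson) 95% interval: 0% to 84% for 0/2 and 16% to 100% for 2/2.
- Section 11.2 sets a criterion of establishing a true seroconversion rate of at least 30% with 95% confidence. Even at 2/2 the lower limit is √0.025 = 15.8% (two-sided) or √0.05 = 22.4% (one-sided), so a group of 2 cannot meet it.
- SAP Table 4.3 has seven pairs: 1v2, 3v4, 5v6, 1v5, 3v5, 2v6 and 4v6. Three use Group 5 (5v6, 1v5, 3v5). Two more (2v6, 4v6) are affected if the ten affected Group 6 subjects are not analysed. Pairs 1v2 and 3v4 are untouched.

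**The case against.** The other side has real points.

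- **The plan's arithmetic works under full enrolment.** 72 × 10/12 is 60. That stands: the fault is an unstated condition and too strong a verb, not a wrong product.
- **The documents do not say how many affected Group 6 subjects finished.** A reader might infer that all ten are lost and that the plan's own figures cap completers at exactly 52. Section 11.2 gives completion of the series as the purpose of replacement. Appendix B speaks of completed vaccinations only for Groups 2 and 4 and, on one reading, the Group 6 sentinels. Both point towards k = 0, but neither says so, and Appendix B attaches 36 to a description that covers 12 + 12 + 2 = 26. The supportable cap is 52 + k.
- **This is a Phase 1 trial not sized to compare groups.** Section 11.2 and SAP 5 say so, and the primary objective is safety, analysed in everyone given one dose: 62 subjects even without the last 20. That stands as to power, and nothing here asks for power. It does not reconcile a guarantee with an enrolment rule in the same protocol.
- **A reader might infer that the combination and route objectives would be lost.** That goes too far. The monovalent route comparisons (1v2, 3v4) are unaffected. Pairs 2v6 and 4v6 survive if the affected Group 6 subjects are analysed, which the one-dose inclusion rules in Protocol 11.7 and SAP 6.3.2 allow when serology exists.
- **The 6 × 12 slip is editorial.** Agreed: the Synopsis and 6.3.1 correctly give Group 6 as 22.

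**Conclusion.** The point holds as a wrong statement about the design. If the final 20 are not enrolled, at most 52 to 62 subjects can complete, depending on k, and about 10 per group fails for any k because Group 5 has 2. In that case the three pairs that use Group 5 carry almost no information. If the 20 are enrolled, 60 is a reasonable expectation but not assured: at the plan's implied retention the chance is about 0.58.

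The head counts come from the documents, apart from k. The probabilities assume k = 0, one common dropout rate and independent losses; any k above 0 would raise the total. They are planning figures, since the sponsor already knows the outcome for subjects dosed by March 2020. The documents give no likelihood that the 4-month condition will fail, so none is claimed here.

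**What to change.** In Protocol 11.2, 6.2, 7.5.4 and the Synopsis:

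1. Replace *will ensure* with wording such as: *is expected to give about 60 completers if about 10 of 12 per group complete*.
2. State the completer count for both cases, with the actual k taken from the dosing records. For example: *If the final 20 subjects are enrolled, 72 + k can complete. If they are not, 62 will have been enrolled, at most 52 + k can complete, and Group 5 will have 2 subjects and could not meet the 30% seroconversion criterion of Section 11.2.*
3. In 6.2 and 7.5.4, change six groups of 12 totalling 82 to five groups of 12 and one of 22. The 72 in 11.2 is correct and stays.

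The cost is wording in four places and one look-up of k. No subjects are added, and the planned SAP tests do not change. The stated size becomes less favourable, but it then agrees with the enrolment rule.

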11.1. Description of Statistical Methods

Descriptive analysis of safety and reactogenicity outcomes will include all subjects who meet the eligibility criteria, receive at least one vaccination, and for whom safety data are available. Summary tables will be created in which incidence, severity, and relationship to the use of investigational product of individual solicited local and systemic signs, symptoms, or trending unsolicited events are delineated by study group, severity, gender, and overall. Unsolicited AEs and SAEs will be analyzed in a similar fashion.

Descriptive analysis of immunogenicity outcomes will include all subjects who meet the eligibility criteria, receive at least one vaccination, and for whom serological data are available. The primary analysis variable will be the proportion of seropositive subjects (defined as $\text{PsVNA50} \geq 1:20$) at each scheduled time point for which blood samples are taken (eg, Days 0, 28, 56, 84 and 140), and the final overall rate of seroconversion over all scheduled time points to study completion for each study group. Seroconversion is defined as a post-vaccination HTNV- or PUUV-specific titer of $\geq 1:40$, or a minimum four-fold rise compared to baseline titer and all study volunteers will begin the study with a baseline titer < 20 (ie, seronegative). For each study group, a binomial proportion and 95% confidence interval (CI) will be calculated. The secondary analysis variable will be geometric mean titers (GMT), with 95% CIs, of the PsVNA50 for HTNV- and PUUV-specific antibodies at each scheduled time point for which blood samples are taken for each study group and over all time points for each study group. GMT, standard errors, and 95% CIs will be calculated using log-transformed titers. For titers below the lower limit of detection (< 20), the value will be transformed to a value equal to the lower limit of detection (ie,

20) divided by the square root of 2, which equals 14.1. Exploratory objectives may evaluate PsVNA80 titers, which may be calculated for informational purposes, and may evaluate PsVNA50 titers against related Seoul and Dobrava viruses.

For hematology and serum chemistry tests, any clinically significant changes from baseline value will be identified. The median, interquartile range, and normal values for each laboratory value (as determined by the contract laboratory) will be reported for each treatment group for each specimen collection point.

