11.3. Level of Significance to Be Used

All statistical analyses will be made using a two-tailed $\alpha = 0.05$.

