5. SAMPLE SIZE CONSIDERATIONS

Because this is a pilot study, all analyses are exploratory. The group sample sizes of up to 12 subjects thus were chosen without the intention that group differences will be detected with a sufficient power.

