9. IMMUNOGENICITY

Descriptive analysis of immunogenicity outcomes will include all subjects who meet the eligibility criteria, received at least one vaccination, and for whom serological data is available. The primary analysis variable is the proportion of seropositive subjects ($\text{PsVNA50} \geq 1:20$) at each scheduled time point (e.g., Days 0, 28, 56, 84, 140, and 220) (Table 3.1), and the final overall rate of seroconversion over these timepoints. Additionally, the proportion of subjects to ever reach seropositivity will be provided at each scheduled time point for which blood samples are taken (Table 3.2). Duration of seropositivity is presented in Table 3.3. For each study group, a binomial proportion, and corresponding 95% CI will be calculated. Chi-squared test or Fisher's exact test will be used to examine the association between group and each binary outcome of interest. Figures 1.1 and 1.2 will present percentages of subjects with seropositivity and seroconversion, by time point by group.

The secondary analysis variable is geometric mean titers, with 95% CIs, of the PsVNA50 for HTNV and PUUV specific antibodies at each scheduled time point (e.g., Days 0, 28, 56, 84, 140, and 220), and will be presented in Figure 1.5. Geometric mean titers, standard errors, and 95% CIs will be calculated using log-transformed titers, titers below the lower limit of detection (<20) will be transformed to a value equal to the lower limit of detection divided by the square root of 2 ($20/\sqrt{2} = 14.1$ Hornung & Reed (1990) (Table 3.4). PsVNA80 titers may be calculated from existing data for information. The reciprocal of the dilution that results in an 80% decrease in luciferase activity is the PsVNA80 titer. PsVNA using other hantavirus PsV (eg, Seoul virus, Dobrava virus) may also be performed to evaluate levels of cross-neutralizing antibodies. Additionally, Fisher's exact test will be used to examine the difference in the proportion of participants to ever seroconvert between each two groups (Table 4.3).

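### Protocol 11.2 sets the seroconversion threshold for 12 subjects at 8.4, which cannot be observed, and names no interval; under the exact two-sided 95% interval the count is 8 of 12.

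*Protocol*

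**What the plan says.** Protocol Section 11.2 describes six groups of 12, with about 10 per group expected to complete all vaccinations, and ends with the statement that "at least 7/10 or 8.4/12 subjects must seroconvert to establish a true seroconversion rate of no less than 30% with 95% confidence". It is the only inferential figure in the section, and Section 4.8 sends the reader there for the statistical justification of the sample size.

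The interval behind the statement is not given. Section 11.3 fixes sidedness ("All statistical analyses will be made using a two-tailed" alpha of 0.05). Section 11.1 says "For each study group, a binomial proportion and 95% confidence interval (CI) will be calculated", and SAP Section 9 says much the same: "For each study group, a binomial proportion, and corresponding 95% CI will be calculated". Neither names a method. SAP Section 5 gives no threshold and says "Because this is a pilot study, all analyses are exploratory".

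**The concern.** There are two linked faults.

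- **The count.** A number of seroconverters is a whole number, so 8.4 of 12 cannot occur. It equals 0.70 x 12. A confidence limit does not scale that way: at the same observed proportion, a larger group gives a narrower interval, so the proportion needed to clear 30% should be no higher at 12 than at 10. Because the sentence sets a minimum, its literal meaning is 9/12.
- **The method.** With 10 to 12 subjects, the common binomial intervals differ enough to change which counts clear 30%. Without a named interval the threshold cannot be reproduced, and the group intervals planned in SAP Tables 3.1, 3.2 and 4.3 are left open in the same way.

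At stake are the accuracy of the sample-size justification and how a reader sets a group's result against 30%. No decision rule is involved.

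**Working it through.** **Inputs.** Benchmark rate 30%, 95% confidence, stated counts 7/10 and 8.4/12 (Protocol 11.2); two-tailed alpha of 0.05 (Protocol 11.3); group sizes 12 enrolled and about 10 completing (Protocol 11.2). The interval method is not given, so several were tried.

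**Step 1: where 8.4 comes from.** 7/10 = 0.70, and 0.70 x 12 = 8.4.

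**Step 2: reproduce 7/10.** The exact lower limit for x of n is the 2.5% quantile of Beta(x, n - x + 1). It exceeds 30% when P(X >= x | n, 0.30) is below 0.025.

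- 6/10: limit 26.2%; P(X >= 6) = 0.0473. Fails.
- 7/10: limit 34.8%; P(X >= 7) = 0.0106. Passes.

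The minimum is 7/10, as the protocol states.

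**Step 3: same method at n = 12.**

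- 7/12: limit 27.7%; P(X >= 7) = 0.0386. Fails.
- 8/12: limit 34.9%, full interval 34.9% to 90.1%; P(X >= 8) = 0.0095. Passes.
- 9/12: limit 42.8%, full interval 42.8% to 94.5%; P(X >= 9) = 0.0017. Passes, but is stricter than needed.

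The minimum is 8/12 (67%), against 9/12 (75%) on the literal reading of 8.4.

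**Step 4: other intervals.** Smallest count whose 95% lower limit exceeds 0.30, with that limit and, in brackets, the limit for one fewer. All are two-sided except the last row.

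| Interval | n = 10 | n = 12 |
|---|---|---|
| Exact | 7: 0.348 (0.262) | 8: 0.349 (0.277) |
| Wald, continuity-corrected | 7: 0.366 (0.246) | 8: 0.358 (0.263) |
| Wilson, continuity-corrected | 7: 0.354 (0.274) | 8: 0.354 (0.286) |
| Wald | 7: 0.416 (0.296) | 7: 0.304 (0.217) |
| Mid-P | 7: 0.380 (0.291) | 7: 0.302 (0.234) |
| Wilson | 6: 0.313 (0.237) | 7: 0.320 (0.254) |
| Agresti-Coull | 6: 0.312 (0.237) | 7: 0.319 (0.254) |
| Jeffreys | 6: 0.304 (0.224) | 7: 0.312 (0.243) |
| Exact, one-sided | 6: 0.304 (0.222) | 7: 0.315 (0.245) |

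Five of the nine reproduce 7/10. Of those, three give 8/12 and two give 7/12. None gives 9/12. The protocol's 7/10 therefore narrows the choice of method but does not settle it.

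**The case against.** The strongest reply is that nothing depends on this sentence. The SAP calls all analyses exploratory, Protocol 11.2 says the trial is not designed to show group differences, Section 11.4 sets no statistical stopping criteria, and the 30% benchmark appears nowhere in the SAP or its table shells. Rounded to the nearest whole number, 8.4 is 8, the very count the exact method gives; even 9/12 is sufficient, only stricter than necessary. All of this stands, and it is why the consequence is minor. It does not make the sentence right: a stated minimum should not need rounding down before it can be used.

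A second reply is that the exact interval is inferred. That also stands. Section 11.3 fixes sidedness but not method, so 8/12 is conditional on the exact interval or one of the two continuity-corrected intervals that agree with it.

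A third is that a correction for n = 10 and n = 12 leaves other denominators open: a group may end with 11, and Group 6 may enroll 22. By the exact two-sided method these need 7/11 (lower limit 30.8%; 6/11 gives 23.4%) and 12/22 (32.2%; 11/22 gives 28.2%). This is a useful extension. It follows once the interval is named and does not undermine the counts for 10 and 12.

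**Conclusion.** The point holds. 8.4 of 12 is not an observable count, and no interval is named in the protocol or the SAP. If the exact two-sided 95% interval is intended, which fits both the 7/10 and the two-tailed alpha, the threshold is 8/12.

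The size is zero or one subject in 12: zero if 8.4 is rounded to 8, one if it is read literally as 9. The literal error is conservative and changes no planned decision or table. The missing method has a visible effect at one count: 7/12 has a lower limit of 27.7% by the exact method, 30.4% by Wald and 32.0% by Wilson, so the same result can be reported as below or above the benchmark. Choosing the interval after seeing the data should be ruled out.

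The certain part is the non-integer count and the unnamed interval; the value 8 rests on the assumed method.

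**What to change.** Replace the last sentence of Protocol 11.2 with: *At least 7/10 or 8/12 subjects must seroconvert for the lower limit of the exact (Clopper-Pearson) two-sided 95% CI to exceed 30%.* Name the same interval in SAP Section 9 for the seropositivity and seroconversion proportions. It would help to add that the same rule applies to whatever number is analyzed, which covers 11 and 22. If another interval was intended, name it and give its own pair of whole-number counts.

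The cost is one protocol sentence and one SAP phrase, with no change to design, enrollment or procedures. Protocol 11.6 and 14.1.2 require amendment and approval steps, so the protocol correction can travel with the next amendment. The SAP phrase can be set when the SAP is finalized before database lock, as Protocol Section 11 provides.
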